### Side Effects of Conventional Treatments

At present, as there is little difference between treatments in terms of cancer control in the short to medium term, much of the decision making process that governs treatment allocation is based on the differences in the side-effect profiles associated with the various interventions. Table 1 describe the side effect profiles for RP, EBRT and brachytherapy.

	30 day mortality (%)	Major Bleeding (%)	Early Urinary Retention (%)	Stress Incontinence (%)	Bladder Outlet Obstruction (%)	Erectile dysfunction (%)	Proctitis (%)	Recto-urethral fistulae (%)
RP	0-2.1	1-11.5	3	4-50	2-9	29-100	-	0.3-15.4
EBRT	0-1	0	4.5	5.3	27	55	8	0-0.6
Brachy	0	0	1.5-22	0-19	-	40	5-21	0.4-8.8

Table 1: Summary of complications following RP, EBRT and brachytherapy. Data source: European Association of Urology Guidelines (Heidenreich, Bolla et al. 2010).

### Alternatives to conventional therapies

As radical treatments carry the potential for significant short, medium and long-term morbidity such as urinary leakage, erectile dysfunction and radiotherapy toxicity, there has been interest in developing alternative ablative therapies in an attempt to reduce treatment burden whilst retaining cancer control, and to avoid the psychological morbidity associated with surveillance. A number of such technologies have been described and each one is at a different stage in its evaluation and application to clinical practice. These new technologies have been introduced in a fairly haphazard manner and as such, the evidence for their use is varied. A further important consideration is the rapid evolution of the technologies over time, with constant new developments in order to improve energy delivery, targeting, safety and imaging.

### High Intensity Focused Ultrasound (HIFU)

HIFU uses ultrasound energy focused by an acoustic lens to cause tissue damage as a result of thermal coagulative necrosis and acoustic cavitation. The procedure is performed using a transrectal approach and may be performed under general or spinal anaesthesia as a day case procedure. A transrectal probe incorporating an ultrasound scanner and a HIFU treatment applicator is inserted. The probe emits a beam of ultrasound, which is focused to reach a high intensity in the target area. Absorption of the ultrasound energy creates an increase in temperature, which destroys tissue. A cooling balloon surrounding the probe protects the rectal mucosa from the high temperature.

Two systematic reviews of HIFU in the treatment of prostate cancer have been published recently (Lukka, Waldron *et al.*, Warmuth, Johansson *et al.*). Warmuth *et al.* (Warmuth, Johansson *et al.*) identified 20 uncontrolled prospective case series, totalling 3018 patients (2806 primary therapy & 211 salvage therapies). They concluded that for all HIFU procedures, the biochemical disease free rate at 1, 5 & 7 years was 78-84%, 45-84% and 69% respectively. The negative biopsy rate was 86% at 3 months and 80% at 15 months. Overall survival rates and prostate cancer-specific survival rates were 90% and 100% at 5 yr and 83% and 98% at 8 yr, respectively.

Adverse events included complications of the urinary tract (1–58%), erectile function (1–77%), the rectum (0–15%), and pain (1–6%). Lukka *et al.* (Lukka, Waldron *et al.*) found that there were no adequate randomised controlled trials or meta-analyses and concluded that the current evidence on HIFU use in prostate cancer patients is of low quality, rendering it difficult to draw conclusions about its efficacy.

### Cryotherapy

Cryotherapy is the localised destruction of tissue by extremely cold temperatures followed by thawing, and may be performed under general or regional anaesthesia. A warming catheter is initially inserted into the urethra to prevent it being damaged by low temperatures. Cryoneedles or probes are inserted into the prostate via the perineum, using image guidance. Temperature monitor probes may also be placed percutaneously through the perineum. Argon gas is circulated through needles or probes, generating very low temperatures and causing the formation of ice around the prostate with profound tissue destruction. Newer cryotherapy techniques allow these needles to be removed or repositioned so that the frozen zone conforms to the exact size and shape of the target tissue.

In 2008, a Cochrane Library review on prostate cryotherapy as a primary treatment was published, recommending RCTs of cryotherapy versus established treatment modalities for early prostate cancer (Shelley, Wilt *et al.* 2007). All eight studies identified were case series and two were retrospective with a total of 1483 patients. At 5 years, overall survival was reported as 89 to 92% in two studies, and disease-specific survival as 94% in one study. The major complications observed in all studies included impotence (47- 100%), incontinence (1.3-19%), and urethral sloughing (3.9-85%), with less common complications of

fistula (0-2%), bladder-neck obstruction (2-55%), stricture (2.2-17%) and pain (0.4-3.1%). Most patients were discharged the following day (range 1-4 days). Since then, one Canadian RCT, comparing cryotherapy with EBRT as primary therapy for localised prostate cancer in over 200 men, was reported (Donnelly, Saliken et al.). With a median follow up period of 100 months, no significant difference in disease progression was observed between the two arms. However, due to recruitment difficulties, the study was closed before the target accrual was reached.

#### Vascular Targeted Photodynamic therapy

Vascular-targeted photodynamic therapy (VTP) uses light to activate an intra-venously administered photosensitizing drug to produce instantaneous vessel occlusion and subsequent tissue necrosis. The light is delivered by optical fibres placed transperineally under transrectal ultrasound guidance. VTP treatment is given under general anaesthesia and can be performed as a day case. Only small case series of VTP have been reported in both primary and salvage groups. The initial drug dose escalation studies, followed by a light dose escalation study, were performed in men who progressed following EBRT (Weersink, Forbes et al. 2005, Haider, Davidson et al. 2007, Trachtenberg, Bogaards et al. 2007, Trachtenberg, Weersink et al. 2008). They showed that around 60% of men receiving whole gland treatment at the maximal drug and light doses, had a complete response to treatment. Side effects included two recto-urethral fistulae, one of which required surgical intervention. Urinary side effects tended to last for up to six months. One of the applicants of this proposal reported early results in 40 men with no previous treatment for prostate cancer, with no significant side effects (Arumainayagam, Allen et al.).

#### Other Ablative Technologies

There are a number of other technologies that are under evaluation. None of them have sufficient evidence at this time to be used within this trial. Examples include Radiofrequency Ablation (RFA), which acts by converting RF waves to heat, resulting in thermal damage. Radiofrequency interstitial tumour ablation (RITA) has recently been proposed for treatment of prostate cancer (Djavan, Zlotta et al. 1997, Zlotta, Djavan et al. 1998, Shariat, Raptidis et al. 2005, Tucker, Huidobro et al. 2005).

Interstitial laser photocoagulation (ILP) was reported by Amin *et al.* (Amin, Lees et al. 1993) who described a percutaneous technique for local ablation. Irreversible electroporation (IRE) is a new non-thermal ablation modality that uses short pulses of DC to create irreversible pores in the cell membrane, thus causing cell death (Onik, Mikus et al. 2007, Rubinsky, Onik et al. 2008). This technology is in the early clinical phases of development.

### **3.4. Why is the PART study needed now?**

#### Partial Ablation (Focal Therapy) for prostate cancer

Over decades, the principle of surgical ablation and/or radical treatment for cancer has evolved from total and extensive treatment of the affected organs to a more targeted and focal approach with, apparently, equal if not superior effectiveness, as well as fewer adverse events and improved quality of life. The concept is now evolving in prostate cancer using the promising but largely untested emerging technologies described above. Rather than radical therapy treating the whole gland, the aim is to localise and treat the main focus of cancer. This may minimize morbidity by lowering the chance of damage to the neurovascular bundles responsible for erectile function, and the urinary continence mechanism. Focal therapy can be delivered using the ablative modalities as they can treat discrete areas of tissue, but their long-term oncological effectiveness has not been rigorously tested.

The current evidence for focal therapy for prostate cancer is from non-randomised Phase I and II trials in single centres and from case series with small numbers of patients. Phase I/II studies have demonstrated that as few as 5% of men suffer from genitourinary side-effects after focal therapy, with absence of clinically significant cancer in all treated patients ([name], Freeman et al. , Muto, Yoshii et al. 2008, [name], Sahu et al. 2009, [name], Hindley et al. 2012). In men with intermediate risk disease, the primary role of focal therapy is to avoid total gland treatment, thus reducing side effects with comparable oncological effectiveness. A possible strategy which remains untested, is to use novel technologies to target and treat all clinically significant cancers in the gland focally, with careful follow-up and repeat treatments as necessary (particularly of emerging new lesions detected by biopsy). The strategy may obviate the need for any radical therapies. A key caveat with such a strategy is the risk of progression to metastases in intermediate risk disease and the need for accurate targeting and imaging modalities to direct minimally invasive interventions. Focal therapy relies on accurately assessing the status of the disease in the prostate using imaging and biopsies.

#### Cost-effectiveness evidence of treatment options

Previous reviews of health economics in the treatment for localised prostate cancer resulted in limited evidence on cost-effectiveness of radical treatment options and no evidence to date on the cost-effectiveness of the partially ablative techniques outlined above (Hummel, Paisley et al. 2003, National Collaborating Center for 2008, Hayes, Ollendorf et al. 2010, Hummel, Simpson et al. 2010). [name] team (HTA 10/136/01 <http://www.hta.ac.uk/2808>) have found that the main limitations of the cost-effectiveness models were the low quantity and poor quality of the data available on cancer-related outcomes and long-term adverse events of urinary incontinence, sexual and bowel dysfunction and changing technology over the review period, also based on indirect comparisons, limited UK specific and up-to-date resource use, cost and utility data and finally and most importantly the lack of any reliable evidence of effectiveness.

The treatment of localised prostate cancer remains a contentious clinical area. The PART study will inform the medical community about focal therapy versus surgery for intermediate risk localised prostate cancer. It will detail the absolute benefit of focal therapy, whilst comparing QoL and economic outcomes. Despite the poor quality of the few retrospective case series assessing the relative safety and efficacy of focal therapy, a change in practice has started towards focal therapy due to the reduction in side effects and apparent oncological safety. As retrospective case series are often selected and hence biased, we consider that an RCT is the only method to reliably compare these treatments.

#### Potential risks and benefits

The benefits of the main PART study will be great to the prostate cancer community and to new patients diagnosed with the disease (prostate cancer is the second most common cancer after lung cancer, estimated to account for 14% of all new male cancer cases worldwide in 2008 (<http://www.cancerresearchuk.org/cancer-info/cancerstats/types/prostate>)). It will provide patients, clinicians, healthcare commissioners and providers with reliable evidence on the clinical and cost-effectiveness of focal therapy to inform best practice.

There are potential risks and benefits of both randomised treatments. In the RP arm we anticipate a six-month post-operative mortality of 1-2% and a morbidity of 10-15%. To minimise this risk we are using high-volume surgical units and will only include those with good quality outcome data, prior to trial entry. Similarly focal therapy is not without risk and the centres in this trial have all been involved in early clinical

trials of the technologies. Section 12 outlines the quality assurance measures undertaken in PART relating to surgical and partial ablation delivery.

Potential trial participants will be informed of the study, together with its possible benefits and known risks following their discussion at the central cancer MDT. This will be 2 or more weeks prior to their randomised intervention. Potential participants will be provided with a standard patient information leaflet.

#### 4. OBJECTIVES AND OUTCOME MEASURES

##### STAGE 1:

Objectives	Outcome Measures

Primary Objective Demonstrate the feasibility of recruitment to a randomised trial of PA using HIFU versus RP (surgical comparator) for intermediate risk unilateral prostate cancer.
	
 
- Randomisation of 100 participants within the proposed timelines.
 
- Uptake of consent & randomisation of <math>\geq 50\%</math> among invited, eligible patients.
 

Secondary Objectives
 
 
- Qualitative Recruitment Investigation (QRI) to understand recruitment challenges for this trial and to develop and refine optimal recruitment strategies for Stage 2 of the PART study.
 
- To collect data on quality of life and resource usage to help decide which questionnaires to use for Stage 2 of the PART study
 
- To explore feasibility of and refine data capture instruments to inform health economic evaluation for Stage 2 of the PART study.
 
	
 
- Findings of the Qualitative Recruitment Investigation (QRI)
 

##### STAGE 2:

Objectives	Outcome Measures

Primary Objective
 
 
- To compare treatment failure rates between the two treatment groups.
 
	
 
- Primary treatment failure as demonstrated by the need for whole gland ablation and/or secondary interventions.
 

Secondary Objectives
 
 
- To compare the short, medium and long-term effects of both treatment arms
 
- The effect on Quality of Life and Health Resource Utilisation of both treatment arms
 
- The role of imaging by mpMRI and biopsy protocols in determining suitability of patients for focal therapy
 
	
 
- Short, medium and long-term adverse events related to treatments
 
- Disease progression including development of metastases
 
- Disease-specific and all-cause mortality
 
- Quality of life using conventional questionnaires (IIEF-15, IPSS, EQ-5D-5L, FACT-P, UCLA-EPIC)
 
- The role of imaging by mpMRI and biopsy protocols in determining the suitability of patients for focal therapy using data collected in the CRF.
 

--	--

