## 7.8. Treatment failure

### Radical prostatectomy

In patients receiving RP, primary treatment failure will be defined as a rising serum PSA level reaching  $\geq 0.2\text{ng/ml}$  following initial reduction to  $<0.1\text{ng/ml}$  after surgery; or a failure of serum PSA to reach the level of  $<0.1\text{ng/ml}$  after surgery; or clinical progression to local recurrence/systemic disease.

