### Partial ablation

In patients receiving PA, primary treatment failure will be determined by a combination of repeat prostate biopsies, serum PSA levels and clinical appearance of symptoms/signs suggesting disease progression. Prostate biopsies following PA will determine one of five defined scenarios:

1. negative biopsies, in which case the patient will continue to be followed-up as described;
2. positive biopsy in the originally treated area, in which case the patient will be allowed one additional HIFU treatment before the treatment is classed as having failed;;
3. positive biopsy in the untreated area demonstrating a new focus of intermediate risk disease, in which case the patient will be offered additional partial ablation in this area.
4. positive biopsies in any area of the prostate demonstrating low-risk low-volume disease, in which case the patient will not require additional treatment and follow-up will continue as described;
5. positive biopsy following 2 consecutive treatments in any area of the prostate, in which case the treatment will be deemed as having failed.

If follow-up biopsies demonstrate high-risk disease at any point, this will be considered as primary treatment failure and patients will be offered whole gland treatment according to standard of care.

In the presence of primary treatment failure as described above, the patient will be re-staged using pelvic cross-sectional imaging. Patients will be fully informed of their disease status, grade, clinical stage and the treatment options, such as salvage external beam radiotherapy. Regardless of decisions about additional interventions, patients will continue to be followed up and analysed within the trial in accordance with 'intention-to-treat', with full documentation of subsequent treatments.

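### The Stage 2 primary endpoint is defined one way in Section 4 and another in Section 7.8, and the size of the treatment difference, and so the power, depends on which applies

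*Protocol*

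**What the plan says.** The synopsis and the Stage 2 table in Section 4 define the primary outcome in the same words for both arms: "Primary treatment failure as demonstrated by the need for whole gland ablation and/or secondary interventions". The secondary interventions are not defined.

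Section 7.8 defines the same term again, by arm.

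- **Radical prostatectomy (RP):** "In patients receiving RP, primary treatment failure will be defined as a rising serum PSA level reaching" 0.2 ng/ml or more after an initial fall below 0.1 ng/ml. Never falling below 0.1 ng/ml, and clinical progression, also count. No intervention is required.
- **Partial ablation (PA):** "primary treatment failure will be determined by a combination of repeat prostate biopsies, serum PSA levels and clinical appearance of symptoms/signs suggesting disease progression". Five biopsy scenarios follow, and high-risk disease on any follow-up biopsy is failure.
  - Scenario 2, positive biopsy in the treated area: "in which case the patient will be allowed one additional HIFU treatment before the treatment is classed as having failed".
  - Scenario 3, new intermediate-risk focus in the untreated area: "in which case the patient will be offered additional partial ablation in this area", with no statement that this is failure.
  - Scenario 4: "positive biopsies in any area of the prostate demonstrating low-risk low-volume disease, in which case the patient will not require additional treatment".
  - Scenario 5: "positive biopsy following 2 consecutive treatments in any area of the prostate, in which case the treatment will be deemed as having failed".

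Section 7.8 then says that men stay in the intention-to-treat analysis whatever is decided about further treatment, so failure is declared before that decision.

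Section 10.1 bases the Stage 2 power on failure rates of 25% and 35% and says it will be reviewed using the failure rates in the first 100 men. Section 10.3 analyses time to primary treatment failure by logrank methods. Neither says which definition applies.

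**The concern.** The primary outcome should assign every randomised man to event or non-event by one rule. Here two rules carry one name, and the men they classify differently are not rare by construction: repeat ablation is a built-in part of the PA strategy, and a PSA threshold can be crossed without further treatment.

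Three things depend on the choice: the primary logrank comparison, the reading of the 25% and 35% planning rates, and the review of Stage 2 power, which uses failure rates observed in Stage 1. The Stage 1 men also roll into Stage 2. If the choice is left until outcomes have been seen in an open-label trial, it could be influenced by them.

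**Working it through.** **Step 1. The same man under each section**

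| Man | Section 4, plain reading | Section 7.8 |
|---|---|---|
| PA, one repeat HIFU, then negative biopsies | Failure (had a secondary intervention) | Not failure (scenario 2) |
| PA, new focus ablated, then negative biopsies | Failure, if additional ablation is a secondary intervention | Not called failure (scenario 3) |
| RP, PSA at least 0.2 ng/ml after an initial fall, no further treatment | Not clearly failure | Failure |
| PA, low-risk low-volume positive biopsy after two consecutive treatments | Not clearly failure | Scenario 4: no further treatment, follow-up continues. Scenario 5: failure |
| Randomised, received neither RP nor PA | Can be assessed | No criterion, since both rules are written for men who receive the treatment |

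**Step 2. Reproducing the plan's own figure (Section 10.1)**

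Inputs: 25% and 35%, two-sided 0.05, 80% power, 800 men randomised 1:1, 10% drop-out. This leaves 800 × 0.9 = 720 men, or 360 per arm.

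n per arm = [1.960 × √(2 × 0.30 × 0.70) + 0.842 × √(0.25 × 0.75 + 0.35 × 0.65)]² / 0.10² = 329, so 658 in total and 658/0.9 = 732 after drop-out.

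With continuity correction: 349 per arm, 698 in total, 698/0.9 = 776. Power at 360 per arm is 83.5% without the correction and 81.4% with it.

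Logrank check: hazard ratio = ln(0.65)/ln(0.75) = 1.497. Expected events = 360 × 0.25 + 360 × 0.35 = 216, against 193 needed (Schoenfeld); power 84.3%.

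The stated 80% with 800 men therefore holds for a true difference of 25% against 35%.

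**Step 3. What changes with the definition**

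In percentage points of the arm concerned:

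- r = PA men re-ablated who never meet Section 7.8 failure;
- x = RP men who meet the PSA rule with no further intervention;
- y = PA men who fail Section 7.8 with no further intervention.

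The protocol gives none of these, so the values below are assumptions chosen to show a range. RP men who have a secondary intervention without meeting Section 7.8 are taken as none.

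From Section 4 to Section 7.8, the PA rate becomes PA − r + y and the RP rate becomes RP + x. Hence

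difference (7.8) = difference (Section 4) − r − x + y.

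*(a) 25% and 35% are Section 4 rates.* The difference under Section 7.8 is 10 − r − x + y:

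| r | x | y | PA | RP | PA − RP | Power, 360 per arm |
|---|---|---|---|---|---|---|
| 0 | 0 | 0 | 35% | 25% | +10 | 83.5% |
| 5 | 0 | 5 | 35% | 25% | +10 | 83.5% |
| 5 | 0 | 0 | 30% | 25% | +5 | 32% |
| 0 | 5 | 0 | 35% | 30% | +5 | 30% |
| 10 | 0 | 0 | 25% | 25% | 0 | no difference to detect |
| 10 | 5 | 0 | 25% | 30% | −5 | reversed |
| 15 | 5 | 0 | 20% | 30% | −10 | reversed |

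The sign reverses only if r + x − y exceeds 10.

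*(b) 25% and 35% are Section 7.8 rates.* The difference under Section 4 is 10 + r + x − y. With y = 0 it can only widen against PA: r = 10, x = 0 gives +20; r = 10, x = 10 gives +30. It reverses only if y exceeds 10 + r + x.

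**The case against.** The best defence is that Section 4 is a summary and Section 7.8 its operational form. Section 4 speaks of need for an intervention, not receipt of one, and a short objective followed by measurable criteria is ordinary protocol structure. Section 7.8 is explicit that a repeat HIFU in the treated area precedes failure, and Section 3.4 describes a focal strategy in which treatment may be repeated. On this view the fault is a missing cross-reference.

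Part of this stands: the two texts could be meant to agree, so calling them irreconcilable would go too far. But nothing says that Section 7.8 operationalises Section 4 or that repeat ablation is excluded from secondary interventions. Even if both were granted, the conflict between scenarios 4 and 5 would remain, as would the lack of a criterion for men who receive neither treatment.

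It is also fair that arm-specific detection follows partly from one arm keeping the prostate, and that need for further treatment is judged by clinicians who know what was given. Neither definition is plainly superior, so the choice between them is not for this review.

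**Conclusion.** The inconsistency is real and affects the primary endpoint. What follows from the documents is that the size of the treatment difference, and hence the power, depends on an unstated choice: 10 − r − x + y or 10 + r + x − y points according to which definition the planning rates follow. The examples rest on assumed values of r, x and y.

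Three stronger readings are tempting but not supported.

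- **That the choice of definition reverses the result.** A reader might take 35% as the 36-month rate of positive biopsies under a constant hazard, with biopsies only at 12 and 36 months. That gives 13.4% first positive at 12 months, and so at most 13.4% failing Section 7.8 against 25% in RP. But Section 10.1 attaches no time point to 35% and does not say which definition it follows. The model also holds RP at 25% under both definitions and sets to zero the other routes to PA failure (high-risk histology, PSA, symptoms or signs). The HIFU re-treatment strategy is in Trial Specific Instructions that are not shown. Reversal is possible only under the conditions in the working, and in case (b) the gap mostly widens against PA.
- **That men who reject their allocation have no endpoint.** The Section 7.8 criteria attach to treatment received, so a man randomised to PA who has RP can be judged by the RP rule and analysed in the PA arm. The gap is clear only for men who receive neither.
- **That 800 is the wrong number.** It reproduces from its stated inputs.

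**What to change.** Before Stage 2 opens and before the sample-size review:

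1. State one governing definition of primary treatment failure in the synopsis, Section 4 and Section 7.8, applied to all randomised men, including those who receive neither treatment, and timed from randomisation.
2. Define secondary interventions, and say whether the permitted repeat or additional ablation counts.
3. Reconcile scenario 4 with scenario 5.
4. State in Section 10.1 which definition the 25% and 35% rates use, and use the same one when Stage 1 failure rates feed the power review.
5. Prespecify the other definition, with repeat ablation counted the other way, as a sensitivity analysis.

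Which definition governs, and how the clinical scenarios are classified, are for the trial team to reconcile. The cost is a wording amendment, the agreement needed to make it, and one extra analysis. No new data are needed.
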